7.2.10 Rate of relapse/recurrence of specific opportunistic infection or bacterial infection

through week 48

Endpoint

The endpoint is the rate of relapse/recurrence of specific opportunistic infection or bacterial infection through week 48.

Descriptive statistics and graphical representation

The analyses will be performed with the mITT population and DPS1. Data will be summarized with the number and percentage of participants with relapse/recurrence of specific opportunistic infection or bacterial infection through week 48.

Statistical methodology

The rate of relapse/recurrence will be estimated by the number of patients with relapse/recurrence divided by the total number patients in ITT population.

The effect of study treatment on the rate of relapse/recurrence of specific opportunistic infection or bacterial infection at week 48 will be assessed using a logistic regression model with treatment group and adjustments for stratification factor (country/group of neighbouring countries and baseline CD4 cell counts (<50 or \geq 50/ μ L)). An adjusted odds ratio (OR) and the associated 95% Confidence Interval (CI) will be calculated.

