5 ELIGIBILITY CRITERIA

5.1 Inclusion criteria

Patients must meet all the following inclusion criteria to be eligible for participation into this study.

1. The ability to understand and sign a written informed consent form (ICF) and must be willing to comply with all study requirements.
2. Male or non-pregnant, non-lactating females[†].
3. Age \geq 18 years.
4. Have documented, untreated HIV-1 infection with either:
 - a) AIDS with any CD4 cell count (AIDS-defining conditions are listed within Appendix 3).

Or

- b) Severe bacterial infection (BI)[‡] and must have a CD4 cell count $< 200/\mu\text{L}$ within 28 days prior to study entry[§].

Or

- c) Any symptoms or no symptoms and must have a CD4 cell count $< 100/\mu\text{L}$ within 28 days prior to study entry and must have an entry HIV viral load > 1000 copies/mL.

Or

- d) Currently receiving treatment for OI^{**}.
 - i. Subjects with other serious OIs, including other AIDS-defining and AIDS-related OIs for which appropriate therapy other than ART exists are eligible, but Investigator approval must be obtained.
 - ii. Current OI treatment can have been discontinued prior to start of ART.

5. Have an entry HIV viral load > 1000 copies/mL
6. Have the ability to take oral medications.

[†] Male and female sex are defined as sex at birth. For transgender participants ≥ 13 years of age who have been on hormone therapy for more than 6 consecutive months, grade haemoglobin based on the gender with which they identify (i.e. a transgender female should be graded using the female sex at birth haemoglobin laboratory values)

[‡] A severe BI consists of any of bacterial pneumonia, IBI or any bacterial infectious disorder with grade 3 severity (severe or medically significant but not immediately life-threatening, see Appendix 2) or requiring unscheduled hospital admission. An IBI is defined as the isolation of a bacterial organism from a normally sterile body site, or for bacterial nucleic acid to be detected at a normally sterile body site. Sterile body sites include blood, cerebrospinal fluid, pleural fluid, pericardial fluid, peritoneal fluid, joint fluid, bone aspirate, or a deep tissue abscess.

[§] Study entry is defined as the start of the screening process

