9.3 Statistical analysis plan

These analyses will assess the efficacy and safety of BIC containing regimen in comparison with the boosted PI containing regimen.

All randomised patients who received at least 1 time any study treatment will be included in the intent-to-treat (ITT) analysis population. Of note patients lost-to follow-up or violating the protocol will not be excluded from the ITT population. Patients who switch treatment to another will be analysed as if they are remained in their initial randomisation group. All participants who are lost to follow-up or discontinued the study when they are endpoint free at time of leaving the study will be censored at the time of leaving the study. We will use time-to-event methods, including Kaplan–Meier survival curves and Cox proportional-hazards models to account for all participants in the analysis. The per-protocol population will include all patients from the ITT population except those who did not fulfil the inclusion/exclusion criteria, who withdrew their consent, gave up, lost to follow-up or discontinued early study medication for any reasons other than any component of the primary endpoint.

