The incidence of hospitalisation will be estimated by the Kaplan-Meier estimate. The Log-rank test will be used to compare the two survival functions. The duration of hospitalisation will be estimated by the cumulative days of hospitalisation during the course of study and will be compared between the 2 groups by using the Mann-Whitney test. The rate of relapse/recurrence will be estimated by the number of patients with relapse/recurrence divided by the total number patients in ITT population. Fisher's exact test will be used to compare the 2 groups.

The frequency of each Grade 2, 3 or 4 AEs, laboratory toxicities, and ART and OI/BI treatment changes and dose modifications due to toxicities and IRIS will be described and compared by group. Fisher's exact test will be used to compare the 2 groups.

The proportion of patients with health care resource use, and emergency room visits will be compared in the two groups with Fisher's exact test. The total inpatient days will be estimated by the cumulative inpatient days during the course of study and will be compared between the 2 groups by using the Mann-Whitney test.

To assess the impact of study treatment on the evolution of QOL at week 48, we will use multiple imputation approach to replace missing values. We will compare the treatment effect on QOL on each of the 5 datasets generated, including the imputed values, and the results will be combined with Rubin's rules. A generalized estimating equation (GEE) model will be used.

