5.2.1 Full Analysis Population

Modified Intention-to-treat (mITT) analysis set: all randomised participants who received at least one dose of study drug. Participants will be included in the analyses according to the planned randomised intervention.

The following data points sets are defined:

- **DPS1:** All observed data will be included in the analysis set regardless of study intervention discontinuation and/or receipt of rescue therapy
- **DPS2:** For participants who discontinue study intervention and/or receive rescue therapy, post-discontinuation or post-rescue observations will be excluded.

The mITT and DPS1 will be used to estimate the primary endpoints and the all secondary endpoints.

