6.3.2 Baseline data

The following demographic characteristics will be summarized by treatment group and overall:

- Age
- Sex
- Child bearing potential among Female
- Participating country
- Ethnicity (e.g White caucasian; White mixed; Asian, Black; Other)
- Population group (AIDS with any CD4 cell count; Severe bacterial infection and CD4 cell count < 200; Asymptomatic with CD4 cell count < 100; Currently receiving treatment for an opportunistic infection)
- Body weight and BMI
- Systolic and diastolic Blood Pressure
- Pulse rate
- Alcohol intake (Does not drink alcohol; Drink alcohol)
- Smokers (Never smoked; Current smoker; Ex-smoker)
- Recreational drug use
- Days from HIV diagnosis to treatment initiation
- HIV RNA viral load, log10 copies/mL and in category (<100,000; 100,000-500,000; >500,000)
- CD4+ count (cells/ μ L) and in category (<50; 50-199; \geq 200) and CD4+ (%)
- CD8+ count (cells/ μ L) and CD8+ (%)
- CD4/CD8 ratio and in category (<0.10; 0.10-0.30; >0.30)
- Positive HBV Antigen; Positive HCV antibody:
- HCV RNA Viral load among those with Positive HCV antibody
- Positive TB testing result
- Red blood cells ($10^{12}/L$);
- White blood cells ($10^{12}/L$)
- Platelet counts ($10^9/L$)
- Haemoglobin (g/dL)
- Haematocrit (%)
- MVC (fl)
- MCH (pg)
- Neutrophils ($10^{12}/L$)
- Lymphocytes ($10^{12}/L$)
- Monocytes ($10^{12}/L$)
- Eosinophils ($10^{12}/L$)
- Basophils ($10^{12}/L$)
- Sodium (mmol/L)
- Potassium (mmol/L)
- Total Protein (mmol/L)
- Total Bilirubin (μ mol/L)
- Indirect bilirubin (μ mol/L)
- ALT (U/L); AST (U/L)
- Albumin (g/L)
- Creatinine (umol/L); Creatinine clearance (eGFR) (mL/min)
- Alkaline phosphatase (U/L)
- Creatine phosphokinase (U/L)
- Calcium (mmol/L)
- Phosphate (mmol/L)
- Urea (mmol/L)

- Chloride (mmol/L)
- Total cholesterol (mmol/L); HDL-cholesterol (mmol/L); LDL-cholesterol (mmol/L); Triglyceride (mmol/L);
- Glucose (mmol/L)
- Resistance mutations at baseline. Drugs resistance mutations will be identified from the Stanford drugs resistance interpretation algorithm (last version at the time of analysis).
<https://hivdb.stanford.edu/dr-summary/mut-scores/NRTI/>;
<https://hivdb.stanford.edu/dr-summary/mut-scores/NNRTI/>; <https://hivdb.stanford.edu/dr-summary/mut-scores/PI/>; <https://hivdb.stanford.edu/dr-summary/mut-scores/INSTI/>.

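### The relapse/recurrence rate in SAP 7.2.10 is taken over all treated patients, including those who entered without an infection, so it reads lower than the relapse risk among patients infected at entry; early exits also count as no relapse

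*Combined protocol and SAP*

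**What the plan says.** SAP 7.2.10 gives the rule: "The rate of relapse/recurrence will be estimated by the number of patients with relapse/recurrence divided by the total number patients in ITT population". It then compares the arms by logistic regression and reports an adjusted odds ratio. Protocol v5.0, section 9.3.3, has the same fraction ("The rate of relapse/recurrence will be estimated by the number of patients with relapse/recurrence divided by the total number patients", again in the ITT population) with Fisher's exact test.

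The two documents name the population differently but mean the same people. Protocol 9.3: "All randomised patients who received at least 1 time any study treatment will be included in the intent-to-treat (ITT) analysis population". SAP 5.2.1, under the name mITT: "all randomised participants who received at least one dose of study drug". Neither requires an infection at entry.

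Eligibility does not require one either. Criterion 4c in protocol v5.0, section 5.1, reads "Any symptoms or no symptoms and must have a CD4 cell count" below 100/µL. Criterion 4a admits AIDS-defining conditions that are not listed as infections, such as Kaposi sarcoma (a neoplasm in SAP Appendix 3) and HIV wasting (a constitutional disease there). SAP 6.3.2 lists the entry groups for the baseline table, among them "Asymptomatic with CD4 cell count < 100; Currently receiving treatment for an opportunistic infection", but no expected split is given anywhere.

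**The concern.** A relapse presupposes a first episode. Dividing by everyone treated gives the burden of relapse in the trial population. It does not give the risk of relapse in patients who had an infection, which is how a relapse rate will be read and compared with other studies.

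The SAP narrows the analysis set for other endpoints that only some patients can reach. Resistance is analysed among failures with a sequence (7.2.3), time to CD4 above 200 among those at or below 200 at baseline (7.2.4), and duration of hospitalisation among those hospitalised (7.2.9). Section 7.2.10 has no such restriction.

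The second issue is follow-up. With a fixed denominator and a binary outcome, a patient who dies or leaves before relapsing counts the same as one followed to week 48 without relapse. Section 5.3 censors lost patients at the last observation, and IRIS and hospitalisation (7.2.7, 7.2.8) are analysed as time to event with follow-up ending at death or exit. Section 7.2.10 gives no rule for such patients.

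**Working it through.** **1. The plan's own figure.** The documents state no relapse rate, at-risk share or power for this endpoint. The only related figure is the planned denominator, and it reproduces from SAP section 4:
- Events for a margin of 1.606 and an expected hazard ratio of 0.909 (two-sided 5%, 80% power, 1:1): 4 × (1.96 + 0.842)² / [ln(1.606/0.909)]² = 97, as stated.
- Evaluable patients: 97 / [(0.25 + 0.23)/2] = 404, as stated.
- With 7.5% drop-out: 404 / 0.925 = 437, against 440 planned (220 per arm).

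**2. The rate.** Let s be the share infected at entry, r their relapse risk, and q the recurrence risk in the others. All three are assumptions.
- Reported rate = s·r + (1 − s)·q.
- Relative shortfall against r = (1 − s)(1 − q/r). This is at most 1 − s, and equals it only when q = 0.

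With r = 10% and q = 0:

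| s | Reported rate | Absolute gap | Relative gap |
|---|---|---|---|
| 30% | 3% | 7 points | 70% |
| 50% | 5% | 5 points | 50% |
| 70% | 7% | 3 points | 30% |
| 90% | 9% | 1 point | 10% |

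With s = 50% and r = 10%, letting q rise:
- q = 1%: reported 5.5%, relative gap 45%.
- q = 2%: reported 6.0%, relative gap 40%.
- q = 5%: reported 7.5%, relative gap 25%.

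**3. The treatment contrast.** Take s = 50%, q = 0, and risks of 20% and 10% among those infected at entry. Over all patients these become 10% and 5%.
- Relative risk: 0.50 in both sets.
- Odds ratio: (0.10/0.90)/(0.20/0.80) = 0.444 at risk; (0.05/0.95)/(0.10/0.90) = 0.474 over all.
- Risk difference: 10 points at risk, 5 over all.
- Power: about 55% with 110 at risk per arm, 51% with 220 per arm.

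At s = 30% and 70% the whole-set odds ratio is 0.485 and 0.462. At risks of 10% and 5% with s = 50%, the odds ratios are 0.474 and 0.487, and power is 29% and 28%. Chance imbalance in s between arms has a 95% limit of 1.96 × √(2 × 0.5 × 0.5/220) = 0.093, about 9 points.

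**4. Early exits.** As an outer limit, suppose 7.5% of patients all leave before any relapse and carry the same 10% risk. The observed risk is 10% × 0.925 = 9.25%. Equal loss in both arms would leave the relative risk unchanged; unequal loss would not.

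**The case against.** The strongest reply is that a whole-population proportion is a legitimate quantity, specified in protocol v1.5 and kept in v5.0, and that it preserves the randomised comparison. That stands: it is wrong only if read as relapse risk among infected patients.

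A reader might infer that the rate is too low by exactly the share without an entry infection. The documents do not support this. The endpoint covers recurrence as well as relapse, and an infection first acquired on study can recur. SAP Appendix 3 requires both episodes of recurrent bacterial pneumonia, and of recurrent Salmonella septicaemia, to occur after enrolment. The SAP cites these criteria for clinical events in 2.2.1, though not expressly for 7.2.10. Under them a patient who entered uninfected can have the event, so the share is a ceiling.

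A reader might also infer that the denominator biases the comparison of arms. Step 3 shows otherwise for relative measures; only absolute measures shrink.

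On early exits, no unequal loss is documented. Protocol 6.5 encourages patients who stop study drug to attend to week 48, and the SAP's DPS1 rule keeps their data. Recurrent AIDS-defining events from day 28 and new severe BI also enter the time-to-event primary endpoint, with component analyses. This lowers the stakes but does not supply a relapse rate, because the AIDS component pools new with recurrent events.

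Finally, the entry-group label is an unsafe guide to who was infected. SAP 6.3.2 calls one group asymptomatic, whereas criterion 4c in protocol v5.0 takes patients with or without symptoms. This affects how the at-risk set is built, but it does not remove the need for one.

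**Conclusion.** The point holds for the descriptive rate and the absolute risk difference. Both fall below their values among patients infected at entry whenever uninfected entrants have the lower risk. The relative shortfall is at most the share without an entry infection. Its size cannot be computed, because the documents give no entry shares and do not define relapse, recurrence or which specific infections count. The 3%, 5% and 7% figures rest on assumed shares, an assumed 10% risk and no events in uninfected entrants.

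The relative treatment effect is little affected. Counting deaths and early exits as no relapse is a separate inconsistency with 5.3, 7.2.7 and 7.2.8. Its effect is small at the planned drop-out if the arms lose patients equally, and unknown if they do not. This is one secondary endpoint, so the primary conclusion is unaffected.

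**What to change.** In SAP 7.2.10:
- Report relapse/recurrence, as n/N by arm, among participants with an OI or severe BI documented before randomisation. Randomisation is at the baseline visit and the trial is open-label, so the cut-off should precede knowledge of the arm. Build the set from the recorded medical history as well as the entry group.
- Keep the mITT proportion beside it, so that recurrences of infections first acquired on study still count.
- State which infections and events count, and whether two on-study episodes are needed.
- Analyse time to first relapse/recurrence to week 48, with early exits censored and death ending follow-up, using the adjusted Cox model of 7.2.7 and 7.2.8. Cumulative incidence with death as a competing event is optional.
- Add a table row showing both denominators. Tables 4 and 8 have no row for this endpoint.

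The cost is SAP wording and one table row, since entry group and history of HIV-associated conditions are already collected. The downside is small: the at-risk subset has fewer patients, so its estimate is less precise.

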8. SAFETY ANALYSES

Endpoints

Safety endpoints include the following endpoints:

- Cumulative incidence of any adverse events (AEs: grade \geq 2), separately grade 2, 3 and 4 AE
- Cumulative incidence grade 3 or AEs
- Cumulative incidence of drug-related AEs (all grade)
- Cumulative incidence of drug-related grade 3 and 4 AEs
- Cumulative incidence of serious adverse events (SAE)
- Cumulative incidence of AE leading to study/treatment
- Cumulative incidence of laboratory toxicities
- Death

Participants with multiple adverse events on a given day will be considered as having one adverse event on that day. Adverse events occurring before the initiation of study treatment (baseline) will not be considered in the analysis.

Descriptive statistics and graphical representation

All analyses on safety endpoints will be performed on the Safety analysis set. All observed data will be included in the analysis set.

Any AE (grade \geq 2), grade 3 or 4 AE, SAE, drug-related SAE, grade 2, 3 and 4 AEs, drug-related grade 3/4 AE, drug-related AEs (all grade), discontinuation of study/treatment due AEs, laboratory toxicities and death will be summarized with the total number of events, number and percentage of participants with at least one event and the incidence rates per 100 person-years of these events by treatment group (BIC versus DRV/c). The most frequent drug-related grade 3 or 4 AEs will be reported.

Statistical methodology

The incidence rates of each endpoint of interest will be calculated by the total number of events from baseline to week 48 visit divided by the total number of person-years. In this analysis, the entire

follow-up will be considered (i.e. follow-up will begin at baseline and continue until the week 48 visit, study discontinuation or death, loss to follow-up; whichever occurs first). The duration in years of participation for each subject will be calculated by the difference between the date of the last observation and the date of date of study treatment initiation plus one, divided by 365.25. The person-years is the total sum of the number of years that each member of a study population has been under observation.

The incidence rates of each endpoint will be compared between the treatment groups (BIC versus DRV/c) with a Poisson regression model adjusted for stratification factor (country/group of neighbouring countries and baseline CD4 cell counts (<50 or \geq 50/ μ L)). The incidence rates ratio and the associated 95% confidence interval will be calculated. All P-values will be two-tailed with a significant level at 5%.

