1.2.2 Risk/Benefit Assessment for the Study

All patients with HIV-1 infection should receive effective ART. Potential risks associated with all classes of ARVs include IRIS. The risk of class effects is considered to be low. Important identified risks appropriately managed by study inclusion/exclusion criteria as well as through close clinical and laboratory monitoring during the study, are as follows: hypersensitivity reaction, including liver injury, and allergy to any components of the regimens. Interim data will also be reviewed by an independent data monitoring committee.

Potential benefits may include provision of a new ART that is not currently available, and which may have fewer side effects than alternative therapies. The benefits of participation for patients receiving B/F/TAF include provision of a therapy with less DDI due to the non-boosting regimen. Other potential benefits include provisions of fixed dose combination (FDC) therapy, and the knowledge that patient participation will contribute to the body of knowledge of HIV therapies.

Following a chronic 39-week study in monkeys, animals administered the highest dose of BIC (1000 mg/kg/day) had bile duct hyperplasia (increased cell growth) and hypertrophy (increased cell size), and some increased cell growth and inflammation in nearby liver cells. These effects were not seen in monkeys administered the mid-level dose (200 mg/kg/day), and these animals had plasma BIC exposures that were approximately 5-fold above human exposures when given the B/F/TAF FDC. No adverse drug reactions associated with liver or bile duct problems have been identified in humans treated with BIC.

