Darunavir as a component of D/C/F/TAF fix-dose combination can cause transient and usually asymptomatic elevations in serum aminotransferase levels and has been linked to rare instances of clinically apparent, acute liver injury. No dose adjustment of D/C/F/TAF is required in patients with mild or moderate (Child-Pugh Class A/B) hepatic impairment or in patients with estimated glomerular filtration rate according to the Cockcroft-Gault formula (eGFR_{CG}) ≥ 30 mL/min. The most frequent adverse reactions reported were diarrhea, nausea, fatigue, headache, and rash. Darunavir contains a sulphonamide moiety and should be used with caution in patients with a known sulphonamide allergy. Co-administration of D/C/F/TAF and medicinal products primarily metabolised by CYP3A may result in increased systemic exposure to such medicinal products, which could increase or prolong their therapeutic effect and adverse reactions.

The overall benefit-risk assessment for B/F/TAF and D/C/F/TAF is favourable at this time.

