2.4.2 Secondary endpoints/outcomes

- Proportion of patients with HIV-RNA viral load < 50 copies/mL at week 24, 36, 48
- HIV-1 drug resistance at confirmed virological failure (genotype)
- Time to reach CD4 count > 200/ μ L (first measurement)
- Proportion of patients with CD4 cell count < 200 μ L and < 350 μ L at week 4, 8, 12, 24, 36, 48
- CD4/CD8 ratio at week 4, 8, 12, 24, 36, 48
- Incidence of IRIS in the two arms through week 48
- Incidence and duration of hospitalisation, rate of relapse of specific OI/BI through week 48
- Safety and tolerability, measured by Grade 2, 3 and 4 signs and symptoms and laboratory toxicities through week 48
- ART and OI/BI treatment changes and dose modifications due to toxicities and DDI with ART, and IRIS through week 48
- Health care resource use, including total inpatient days and emergency room visits through week 48
- QOL and functional status outcomes, including overall self-reported QOL and functional status compared in the two groups at week 48
- Discontinuation or modification of study medication due to insufficient virological response, resistance mutations at baseline, or resistance mutation development before week 48

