10.1.6 Change from baseline in plasma and urine laboratory parameters

Endpoints

The endpoints are the change from baseline plasma and urine laboratory parameters

Descriptive statistics and graphical representation

The analyses will be performed with the mITT population and DSP1.

Data will be summarised by mean and standard error. The evolution will be described by boxplots for each treatment group at each time point.

Statistical methodology

The changes from baseline in haematology, chemistry, lipid and glycaemia will be compared between the two treatment groups using mixed models for repeated measures with random intercept and slope and spatial power covariance structure due to unequal time intervals between visits, adjusted for country/group of neighbouring countries and baseline CD4 cell counts (<50 or $\geq 50/\mu\text{L}$). The model will include treatment group, time, interaction between treatment group and time, country/group of neighbouring countries and baseline CD4 cell counts (<50 or $\geq 50/\mu\text{L}$). Time will be modelled as categorical variables.

All p-values will be two-tailed, with a significant level of 0.05.

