Mean (95% CI) difference from baseline to week 48			

TABLE 7: SAFETY

	Integrase inhibitor (N=XXX) Person-Year (P-Y): XXX.X			Protease inhibitor (N=XXX) Person-Year (P-Y): XXX.X			P-value
	N of events	N of pts (%)	Incidence rate/100 p-y	N of events	N of pts (%)	Incidence rate/100 p-y	
Any adverse events (AEs : grade ≥2)							
Grade 2							
Grade 3							
Grade 4							
Grade unknown							
Grade 3 or 4 AE							
Drug related AEs							
Drug related grade 3/4 AEs							
dress syndrom (rash)							
IRIS							
IRIS-Kaposis sarcoma							
PML-IRIS requiring hospitalisation							
progressive rash							
transaminitis							
worsening symptoms of Progressive multifocal leukoencephalopathy							
....							
....							
AE leading to the study drugs interruption							
Serious adverse events (SAE)							
Laboratory toxicities							
Death							

TABLE 8. OTHER SECONDARY ENDPOINTS

	Integrase Inhibitor	Protease Inhibitor	Adjusted OR	P-value
	N=XXX	N=XXX	(95% CI)	
Percentage of patients with HIV drug resistance mutations among those with virological failure				
Proportion of patients with ART treatment changes due to toxicities and/or DDI with ART, and/or IRIS through week 48 - due to toxicities - due to DDI - due to IRIS				
Proportion of patients with with health care resource use, including total inpatient days and emergency room visits through week 48				
Proportion of patients with discontinuation or modification of study medication due to insufficient virological response or resistance mutations development before week 48 - for insufficient virological response - resistance mutations development				
Proportion of patients for whom there is a difference in the list of mutations (Stanford list last available version) detected by deep sequencing compared with those detected by population sequencing				

TABLE 9: EVOLUTION OF QUALITY OF LIFE (HEALTH STATUS SCORE) AND HIV SYMPTOMS INDEX

Week	QOL : health status score			HIV Symptoms index score		
	Integrase Inhibitor	Protease Inhibitor	P-value between groups	Integrase Inhibitor	Protease Inhibitor	P-value between groups
	Mean (SD)	Mean (SD)		Mean (SD)	Mean (SD)	
0						
4						
8						
12						
24						
36						
48						
Mean (SD) from baseline to W4						
Mean (SD) from baseline to W8						
Mean (SD) from baseline to W12						
Mean (SD) from baseline to W24						
Mean (SD) from baseline to W36						
Mean (SD) from baseline to W48						

TABLE 10: QUALITY OF LIFE DIMENSIONS: MOBILITY AND SELF- CARE

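### The SAP reports laboratory toxicities as one ungraded row with no analyte, so no output counts participants by arm with graded ALT, AST or bilirubin rises taken from the laboratory values

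*Combined protocol and SAP*

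**What the plan says.** Protocol v5.0, section 2.4.2, lists among the secondary endpoints "Safety and tolerability, measured by Grade 2, 3 and 4 signs and symptoms and laboratory toxicities through week 48". Section 9.3.3 says that graded AEs and laboratory toxicities will be described and compared by arm, and names Fisher's exact test. Protocol v1.5 has the same endpoint and the same analysis sentence.

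SAP 2.2.2 restates the endpoint as Grade 2, 3 and 4 adverse events, treatment-related AEs, AEs leading to discontinuation, and death. Laboratory toxicities are not mentioned there. They return in SAP section 8 as one item, "Cumulative incidence of laboratory toxicities", with no grade, analyte or threshold. In Table 7 they have one row, "Laboratory toxicities". The Grade 2, 3 and 4 rows of that table belong to AEs.

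By event term, section 8 promises only this: "The most frequent drug-related grade 3 or 4 AEs will be reported". The one liver term in Table 7 is "transaminitis", an example row under drug-related grade 3/4 AEs.

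For individual analytes, SAP 10.1.6 states "Data will be summarised by mean and standard error". It adds boxplots by arm and visit and a mixed model for change from baseline. Table 15 has shells for ALT, AST, total and indirect bilirubin and alkaline phosphatase in that form.

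As background, protocol 1.2.2 includes among the important identified risks "hypersensitivity reaction, including liver injury, and allergy to any components of the regimens". Of darunavir it says that aminotransferase rises can occur, usually without symptoms, and that it "has been linked to rare instances of clinically apparent, acute liver injury". Section 1.2.1 reports bilirubin increases in 12% of patients on B/F/TAF, mostly Grade 1 (9%) and Grade 2 (3%).

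**The concern.** The natural question about liver laboratory safety is how many participants in each arm had a worst value of Grade 2, 3 or 4 for ALT, AST or bilirubin. None of the planned outputs answers it.

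The single row adds all analytes and grades together, and the SAP does not say what counts as a laboratory toxicity. The two regimens have different laboratory descriptions in the protocol: bilirubin and creatinine for B/F/TAF, aminotransferases for darunavir. Summed in one row, such patterns can offset each other. Mean changes do not show how many participants had a large rise. Participants may also enter with ALT and AST up to 5 times the upper limit of normal (exclusion criterion 5), so falls in some can balance rises in others.

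At stake is a clear reading of a named secondary safety endpoint. The primary analysis and the sample size are not affected.

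**Working it through.** **Step 1. Each output against the question.** The question is the number of participants by arm, analyte and grade, taken from laboratory values.

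| Output | By arm | By analyte | By grade | Source |
|---|---|---|---|---|
| SAP 8 and Table 7, laboratory toxicity row | yes | no | no | not stated |
| Table 7, Grade 2/3/4 AE rows and SAE row | yes | no | AE rows only | reported AEs |
| Table 7, example terms under drug-related grade 3/4 AEs | yes | by term | 3/4 pooled | reported and attributed AEs |
| SAP 10.1.6 and Table 15 | yes | yes | no | laboratory values |
| SAP 10.1.1, ART changes due to toxicity | yes | no | no | reported changes with reason |

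No line has every property. The data are available: protocol Appendix 1 makes ALT, AST and total bilirubin mandatory at and after baseline, and Appendix 2 names a grading table.

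**Step 2. How a laboratory value becomes an AE.** Protocol 8.2 asks for laboratory changes to be recorded as AEs when they are clinically significant. That is a judgement by an investigator who knows the arm (6.1.5). A usually asymptomatic rise is the kind of value on which such judgements vary.

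**Step 3. What an ungraded row could hold.** This uses the protocol's own bilirubin figures, which come from patients with less advanced disease. For 220 participants, 0.12 × 220 = 26.4 would have a bilirubin increase, of whom 0.09 × 220 = 19.8 would be Grade 1. If the row admits Grade 1, about 20 such participants in one arm could mask a few Grade 3 or 4 ALT cases in the other. The SAP does not say whether it does.

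**Step 4. Illustration of dilution.** The documents give no graded ALT or AST rates for this comparison, so every rate here is an assumption. The calculation is exact power of a two-sided 5% Fisher test with 220 per arm.

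| Assumed graded ALT/AST rate | Expected participants | Power, graded row |
|---|---|---|
| 2% v 4% | 4.4 v 8.8 | 0.15 |
| 1% v 3% | 2.2 v 6.6 | 0.20 |
| 3% v 6% | 6.6 v 13.2 | 0.25 |
| 2% v 5% | 4.4 v 11.0 | 0.31 |
| 2% v 6% | 4.4 v 13.2 | 0.49 |
| 1% v 5% | 2.2 v 11.0 | 0.62 |
| 1% v 6% | 2.2 v 13.2 | 0.79 |

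For a pooled row, suppose a proportion b in both arms has some other, independent laboratory toxicity. The row then shows 1 − (1 − b)(1 − p), where p is the liver rate.

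- b = 20%: for 1% v 6%, 1 − 0.80 × 0.99 = 20.8% and 1 − 0.80 × 0.94 = 24.8%; power 0.14. For 1% v 5%, 20.8% v 24.0%; power about 0.10.
- b = 40%: for 1% v 6%, 40.6% v 43.6%; power 0.08. For 1% v 5%, 40.6% v 43.0%; power 0.06.

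So with 1% v 5% or 6%, the pooled row has about 6% to 14% power, against 62% to 79% for the graded row. Across all the pairs above, the graded row ranges from about 15% to 79%.

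The SAP compares event rates for this row by adjusted Poisson regression, so these figures are not the power of the planned analysis. They show only that pooling dilutes a difference.

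**The case against.** The strongest reply is that laboratory safety is covered by several routes. Clinically significant laboratory changes are recorded as AEs whether or not they are thought drug-related. They then enter the separate Grade 2, 3 and 4 rows, and Grade 4 events go to SAE reporting by default (protocol 8.2 to 8.2.3). A toxicity that interrupts therapy for more than 5 days can be a primary endpoint event, validated by the Clinical Endpoint Committee. ART changes due to toxicity are counted by arm and listed by patient. The boxplots show spread and, as usually drawn, outlying values.

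All of this stands. A reader might infer that liver toxicity would surface only through open-label attribution to study drug; the documents do not support that, because the general graded AE and SAE rows need no attribution. What remains is that these routes start from an unmasked judgement of clinical significance, that none is liver-specific, and that boxplots are not graded counts.

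Three further points stand. The grammar of protocol 2.4.2 leaves some doubt whether the grades govern the laboratory toxicities as well as the signs and symptoms. The identified risk is worded as hypersensitivity that includes liver injury, although the aminotransferase sentence supports the liver point separately. And 9.3.3 supports a comparison by arm with Fisher's test; it does not ask for per-analyte tables or a worst-grade rule.

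**Conclusion.** The gap is real and limited. Followed exactly, SAP section 8 and Table 7 give one undefined, ungraded laboratory row, and no other output counts participants by arm with graded ALT, AST or bilirubin from laboratory values. The protocol's endpoint, on its more natural reading, and its planned comparison by arm are not carried through for laboratory data.

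A reader might also infer that hepatotoxicity is expected to differ between the arms. No section says so: the protocol calls the darunavir rises transient, calls clinical liver injury rare, and does not link the B/F/TAF bilirubin increases to hepatic reactions. The case for the table is that the regimens' laboratory descriptions differ and the planned row cannot separate them.

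The size cannot be taken from the documents. The power range of about 15% to 79% for a graded row rests wholly on assumed rates, and so does the drop on pooling, which also assumes independent background toxicity of 20% to 40%. The textual conclusion needs neither. This should be changed before database lock, but it does not threaten the trial's main result.

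**What to change.** In SAP section 8 and Table 7, keep the pooled row as a summary, state which grades and analytes it includes, and add a table along these lines:

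> For each of ALT, AST and total bilirubin, the number and percentage of participants in each arm whose worst post-baseline value is Grade 2, 3 or 4 on the grading table in protocol Appendix 2, derived from the laboratory values and not from reported AEs.

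State the rule for participants with an abnormal baseline grade, for example by counting only worsening from baseline or by cross-tabulating baseline grade against worst grade. Other mandatory analytes, such as creatinine, are optional. Bring SAP 2.2.2 into line so that laboratory toxicities appear in the restated endpoint.

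Label the table descriptive, with no multiplicity control. If arms are tested, Fisher's exact test is the one that protocol 9.3.3 names.

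The cost is programming one table from values already collected, and more rows to read. No new data, no change in sample size and no change to treatment rules are involved.
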